5.1. Method of Assignment to Treatment

Patients who meet all criteria for enrollment will be randomized in a 1:1:1 ratio (placebo, baricitinib 1-mg, or baricitinib 2-mg) to double-blind treatment at Visit 2 (Week 0).

Randomization will be stratified by disease severity at baseline (IGA 3 or 4).

Assignment to treatment groups will be determined by a computer-generated random sequence using an interactive web-response system (IWRS). The IWRS will be used to assign bottles, each containing double-blind investigational product tablets to each patient, starting at Visit 2 (Week 0) up to and including Visit 14 (Week 88).

6. A Priori Statistical Methods

6.1. Determination of Sample Size

Study JAIW will aim to enroll approximately 450 patients aged ≥ 18 years. The proposed sample size will ensure at least 68% power to detect any differences between the baricitinib 2-mg and placebo treatment groups, assuming a 10% placebo and 20% baricitinib 2-mg response rate for the primary endpoint EASI75 using a Chi-squared test with a 2-sided α level of 0.05. The assumptions are based on what was observed in the Phase 3 monotherapy Studies JAHL and JAHM.

Sample size and power estimates were obtained from nQuery® Advisor 7.0.

6.2. General Considerations

This plan describes a priori statistical analyses to be performed for efficacy, health outcomes, and safety.

Statistical analysis of this study will be the responsibility of Eli Lilly and Company (Lilly). Statistical analyses will be performed using SAS® Version 9.4 or higher.

Not all displays described in this SAP will necessarily be included in the clinical study report (CSR). Not all displays will necessarily be created as a “static” display. Some may be incorporated into interactive display tools instead of or in addition to a static display. Any display described in this SAP and not included in the CSR can be made available upon request.

Statistical tests of treatment effects and confidence intervals (CIs) will be performed at a 2-sided significance level of 0.05, unless otherwise stated (eg, graphical multiple testing strategy in Section 6.6).

Data collected at early termination visits will be mapped to the closest scheduled visit number for that patient if it falls within the visit window as discussed in Section 6.2.3. For by-visit summaries, only visits in which a measure was scheduled to be collected will be summarized.

Any unscheduled visit data will be included at the patient-level listings. However, the data will still be used in other analyses, including categorical analyses for safety analytes and change from baseline to endpoint using modified last observation carried forward (mLOCF) for efficacy analyses.

6.2.1. Reporting Periods

This study will have data locks as described below.

- An unblinded interim lock was executed after all patients have completed the Week 16 visit (Visit 8) or discontinued. As the primary endpoint (Section 4.2.1) and several secondary endpoints (Section 4.2.2) including safety are evaluated at Week 16, a CSR will report these data.

- An unblinded lock occurred to support the 4-Month Safety Update Report. Additional safety locks to support global submissions may also be performed. Clinical study reports will not be developed based on these safety locks.
- There will be several unblinded locks in support of a Data Monitoring Committee (DMC). Additionally, there will be several blinded locks in support of trial level safety reviews and the Periodic Safety Update Report.
- A final lock will be performed after all patients have completed the Post-Treatment Follow-up Visit (Week 108, Visit 801), discontinued permanently, or entered or switched to Study JAIX. An abbreviated CSR will be developed based on this lock.

The scope of this SAP will be to support the Week 16 unblinding interim lock, 4-Month Safety Update database lock, and the final lock.

The Blinding/Unblinding Plan for Study JAIW will outline efforts to ensure the blinding integrity after unblinded transfers.

6.2.2. Analysis Populations

Intent-to-treat (ITT) population: The ITT population analysis set is defined as all randomized patients.

Per-protocol set (PPS) population: The PPS of the ITT population analysis set will include those patients who do not have any identified important protocol violations considered to impact efficacy analyses. Qualifications for and identification of significant or important protocol violations will be determined while the study remains blinded, prior to database lock.

Unless otherwise specified, the efficacy and health outcome analyses will be conducted on the ITT population (Gillings and Koch 1991), which seeks to preserve the benefits of randomization and avoid the issue of selection bias. Patients will be analyzed according to the treatment to which they were randomized. In addition, the primary will be repeated using the PPS population.

W16 Responders population: The W16 responders analysis set is defined as patients who met IGA 0 or 1, have not required rescue therapy prior to Week 16, and continue in the study beyond 16 weeks.

Efficacy will be summarized in 2 efficacy analysis sets:

- Weeks 0 to 16 based on ITT population, and
- after Week 16 to Week 104 based on W16 Responders population.

The long-term summary will include up to 104 weeks. By design all patients continuing past Week 16 of JAIW were responders without rescue mediation. As it is assumed there will be few placebo responders continuing past Week 16, long-term efficacy will be characterized using descriptive statistics after Week 16 up to Week 104 in the final database lock (DBL)

Safety population: The safety population is defined as all randomized patients who receive at least 1 dose of investigational product and who did not discontinue from the study for the reason 'Lost to Follow-up' at the first postbaseline visit. This definition excludes patients with no safety assessments postbaseline so that incidence rates are not underestimated.

Safety analyses will be done using the safety population. Patients will be analyzed according to the treatment regimen to which they were assigned. Analyses of the safety endpoints, many of which are incidence based, will include all patients in the safety population, unless specifically stated otherwise.

The following are the treatment groups for the analysis of safety for Study JAIW for the 16-week interim analyses:

Treatment Group	Definition
Placebo	Placebo at entry to Study JAIW followed to data cut (interim clinical study report [CSR])
Baricitinib 1-mg	Baricitinib 1-mg at entry to Study JAIW followed to data cut (interim CSR)
Baricitinib 2-mg	Baricitinib 2-mg at entry to Study JAIW followed to data cut (interim CSR)

In the rare situation where a patient is lost to follow-up at the first postbaseline visit, but some safety data exists (eg, unscheduled laboratory assessments) after first dose of study drug, a listing of the data or a patient profile will be provided, when requested.

For the unblinded interim lock which is executed after all patients have completed the Week 16 visit (Visit 8) or discontinued, the efficacy analysis included up to Week 16 and the safety analysis will be up to Week 16 and selected analyses up to the data cut date.

For the final DBL, both efficacy and safety summaries will use the Week 16 Responders population. The data will be summarized from Week 16 to the final DBL, according to the treatment regimen to which patients were assigned at Week 16.

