In general, summaries will include the number of patients in the safety population (N), frequency of patients experiencing the event (n), and relative frequency (that is, percentage; $n/N*100$). For any events that are gender-specific based on the displayed PT, the denominator used to compute the percentage will only include patients from the given gender.

In an overview table, the number and percentage of patients in the safety population who experienced death, an SAE, any TEAE, discontinuation from the study due to an AE, permanent discontinuation from study drug due to an AE, or a severe TEAE will be summarized by treatment group.

The number and percentage of patients with TEAEs will be summarized by treatment group in 2 formats:

- by MedDRA PT nested within SOC with decreasing frequency in SOC, and events ordered within each SOC by decreasing frequency in the baricitinib 2-mg group for the final DBL;
- by MedDRA PT with events ordered by decreasing frequency in the baricitinib 2-mg group.

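### The safety population excludes dosed patients by disposition reason, not by absence of data, so a recorded post-dose event can drop out of the Week 16 and 4-month safety-population tables

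*SAP*

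**What the plan says.** SAP Section 6.2.2 starts from "all randomized patients who receive at least 1 dose of investigational product" and then keeps only those "who did not discontinue from the study for the reason 'Lost to Follow-up' at the first postbaseline visit". Its justification follows at once: "This definition excludes patients with no safety assessments postbaseline so that incidence rates are not underestimated".

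Later in the same section the SAP considers an exception: "In the rare situation where a patient is lost to follow-up at the first postbaseline visit, but some safety data exists" after the first dose, with unscheduled laboratory tests as its example. The patient is not returned to the population. Instead, "a listing of the data or a patient profile will be provided, when requested".

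The reach of the definition is wide. Section 6.2.2 states: "Safety analyses will be done using the safety population". It adds that analyses of safety endpoints "will include all patients in the safety population, unless specifically stated otherwise". Section 6.14 repeats that safety analyses use this population. Section 6.14.2 takes both the count and the denominator of the adverse event summaries from it, including the overview of deaths, serious adverse events and treatment-emergent events.

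**The concern.** The rule and its rationale select different patients, and they diverge in both directions:

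- A dosed patient coded as lost to follow-up at the first postbaseline visit is removed even if a post-dose adverse event or laboratory value is on record.
- A dosed patient with no post-dose assessment who leaves under any other disposition code stays in the denominator.

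So the rule does not do what its rationale says. If an excluded patient had an event, the event disappears from the incidence tables, and incidence is understated by a rule meant to prevent understatement. This matters most for uncommon events, where one case carries much of an arm's estimate. Membership also depends on something that happens after dosing, and that need not be balanced between arms.

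**Working it through.** **The passages side by side**

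1. Exclusion criterion (6.2.2): discontinuation reason and its timing.
2. Rationale (6.2.2): no postbaseline safety assessments.
3. Exception (6.2.2): post-dose data may exist; the remedy is a listing or profile on request, with no return to the tables.
4. Other rules on post-dose data. Section 6.2 keeps unscheduled data for categorical analyses of safety analytes. Section 6.2.3 defines postbaseline, outside by-visit analyses of continuous measures, as every nonmissing measurement after the first dose date. Section 6.14.3 includes unplanned measurements in the treatment-emergent high/low tables. The unscheduled laboratory value given as the example in 6.2.2 is therefore data that these sections would count.
5. Section 6.14.5.1 summarises hepatic elevations among patients with a postbaseline value. The SAP can thus condition on data directly, without a disposition code.

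**Which outputs are affected**

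- Affected: Week 16 and 4-month tables that use the safety population.
- Not affected: skin infections requiring antibiotics as tested in ITT (Table JAIW.6.5); malignancy summaries, which Section 6.14.5.10 says take in all reported cases; final-lock tables, which use Week 16 Responders (6.2.2, 6.14), none of whom could have been lost at the first visit.

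**Size, as an illustration only**

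The SAP gives no figure on this point to reproduce. The arm size of 150 is from Section 5. It agrees with Section 6.1: 10% versus 20% with 150 per arm and two-sided alpha 0.05 gives 68.1% power, against the stated 68%. All event and loss counts below are assumptions.

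Let k be the dosed patients lost at the first visit in an arm of 150, j those among them with a recorded event, and x the events in other patients.

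- SAP rule: x / (150 − k)
- Exclude only patients with no data: (x + j) / (150 − k + j), assuming the other k − j have no data
- All dosed: (x + j) / 150

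| x | k | j | SAP rule | Exclude only no-data | All dosed |
|---|---|---|---|---|---|
| 0 | 1 | 1 | 0/149 = 0.00% | 1/150 = 0.67% | 1/150 = 0.67% |
| 3 | 3 | 1 | 3/147 = 2.04% | 4/148 = 2.70% | 4/150 = 2.67% |
| 3 | 3 | 0 | 3/147 = 2.04% | 3/147 = 2.04% | 3/150 = 2.00% |

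One dropped event costs about 0.6 to 0.7 percentage points (0.67 − 0.00 = 0.67; 2.67 − 2.04 = 0.63; 2.70 − 2.04 = 0.66). The dilution that the rule guards against is 2.04 − 2.00 = 0.04 points when three patients have no data.

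**The case against.** The strongest reply is that the case is rare by the SAP's own account, that it is disclosed, and that serious events stay visible. Section 6.14 says listings include all safety data. Sections 6.14.2.2 and 6.14.2.3 provide listings of serious adverse events, deaths and adverse events leading to discontinuation without waiting for a request. Section 6.14.2.4 provides narratives for notable patients, and Sections 6.14.5.7 and 6.14.5.8 list events sent for adjudication. A patient whose recorded discontinuation reason is an adverse event or death is not excluded at all. All of this stands and keeps the point modest. It does not answer it, because a listed event is still not counted in the incidence tables.

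Four stronger readings are tempting, and the SAP does not support them:

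- *Known events leave every incidence table.* The unaffected outputs named above contradict this.
- *Excluded patients are known to have had events.* Section 6.2.2 speaks conditionally, and its only example is unscheduled laboratory tests.
- *Incidence is necessarily understated.* That holds only if the excluded patient had the event. A patient with only a normal laboratory value leaves the denominator alone, and incidence rises slightly: 3/149 = 2.01% instead of 3/150 = 2.00%.
- *An arm's incidence falls by 25% to 50%.* That presupposes two to four events in the arm, one of them in an excluded patient. The SAP supports neither.

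It is also fair to say that excluding only patients with no data still conditions on post-dose information: an early-lost patient enters because something was recorded. Using all dosed patients avoids this.

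**Conclusion.** The point holds in a limited form. The safety population is defined by a disposition reason that does not match its stated rationale, and the section keeps such patients out even when post-dose safety data exist. In the Week 16 and 4-month tables built on this population, a recorded post-dose event in such a patient would be counted nowhere, although serious adverse events and deaths would be listed.

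The actual effect is unknown, since the SAP gives no counts, and it may be nil. Under the assumed counts, one dropped event costs roughly 0.6 to 0.7 percentage points in an arm of 150, against about 0.04 points of dilution from keeping three patients without data. The exclusion therefore protects against little and can produce the error it is meant to avoid. It is worth correcting, but it does not by itself put the safety conclusions in doubt.

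**What to change.** Define the safety population as all randomised patients with at least one dose. At minimum, exclude a dosed patient only if there is no post-dose safety observation of any kind: adverse event, serious adverse event, death, laboratory value or vital sign, scheduled or not. The all-dosed version is preferable because it does not select on a recorded event.

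In addition:

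- report by arm how many patients the current rule excluded, and how many of them had post-dose safety data;
- make the Section 6.2.2 listing routine instead of on request;
- if any excluded patient had data, rerun the affected Week 16 and 4-month tables.

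**Cost.** The wording change is small. With all dosed patients, incidence is slightly diluted by those without data. The larger cost is timing: Section 6.2.1 shows that the Week 16 and 4-month locks have taken place, both unblinded, so any rerun touches completed outputs and should be labelled as a change made after unblinding. If no excluded patient had post-dose data, a sentence with the counts by arm is enough. Final-lock tables need no change.

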5. Study Design

Study I4V-MC-JAIW (JAIW) is a multicenter, randomized, double-blind, placebo-controlled, parallel-group, outpatient Phase 3 study evaluating the efficacy and safety of baricitinib 1-mg QD and 2-mg QD as compared to placebo in adult patients with moderate to severe AD. The study is divided into 3 periods: a 5-week Screening Period, a 104-week Double-Blinded Treatment Period, and a 4-week Post-Treatment Follow-Up Period.

Approximately 450 patients aged ≥ 18 years who have responded inadequately to or who are intolerant of topical therapy will be randomized at a 1:1:1 ratio to receive placebo QD, baricitinib 1-mg QD, or baricitinib 2-mg QD (approximately 150 patients per group). Patients will be stratified at randomization according to disease severity (IGA 3 versus 4).

The primary and key secondary endpoints are assessed prior to or at Visit 8 (Week 16). At Week 16 those patients who met IGA 0 or 1 and who have not required rescue therapy prior to Week 16 will be allowed to continue in this study. All other patients will be discontinued from this study and may be eligible to enroll in a separate open-label study (Study JAIX). Patients experiencing worsening in disease severity resulting in an IGA score of ≥ 3 after Week 16 of Study JAIW will also have to be discontinued from this study and may be eligible to enroll in the open-label Study JAIX. Patients who complete Week 104 (Visit 15) will have the option to transition to open-label Study JAIX, if eligibility criteria are met regardless of responder status, or continue to the post-treatment follow-up.

Figure JAIW.5.1 illustrates the study design.

Abbreviations: AD = atopic dermatitis; QD = once daily; V = visit; W = week.

- ^a At Week 16, all patients who achieve an IGA 0 or 1 and who have not required rescue therapy before Week 16 will be allowed to continue in this study. All other patients will be discontinued from this study and may be eligible to enroll in the separate open-label Study JAIX.
- ^b Patients who complete this study will be eligible for assessment to enroll in open-label Study JAIX.
- ^c Occurs approximately 28 days after the last dose of investigational product.

Figure JAIW.5.1. Illustration of study design for I4V-MC-JAIW.

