Fisher's exact test will be used to test the difference between each baricitinib dose and placebo in proportion of patients experiencing adverse events (AEs), discontinuation from study drug, and other categorical safety data. Continuous vital signs, body weight, and other continuous safety variables, including laboratory variables, will be analyzed by an ANCOVA with treatment group and baseline value in the model. The significance of within-treatment group changes from baseline will be evaluated by testing whether or not the treatment group LSM changes from baseline are different from zero; the standard error for the LSM change will also be displayed. Differences in LSM will be displayed, with the p-value associated with the LSM comparison to placebo and a 95% CI on the LSM difference also provided. In addition to the LSMs for each group, the within-group p-value for the change from baseline will be displayed.

Time to event will be analyzed using cumulative incidence function with observed values, defining first time reaching the event IGA (0,1), EASI 75, or Itch NRS 4-pt improvement before rescue as onset, treating rescue and discontinuing for lack of efficacy as competing event censor up to Week 16.

For final database lock, the main analysis method for efficacy and health outcomes variables will use descriptive summary per observed and mLOCF data.

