6.14. Safety Analyses

The general methods used to summarize safety data, including the definition of baseline value, are described in Section 6.2.

Safety analyses will include data from , unless otherwise stated, and patients will be analyzed according to the investigational product to which they were randomized at Week 0 (Visit 2). Safety analyses will use the safety population defined in Section 6.2.2.

By-visit summaries will include planned on-treatment visits. For tables that summarize events (such as AEs, categorical lab abnormalities, shift to maximum severity), post-last dose follow-up data will be included. Follow-up data is defined as all data occurring up to 30 days (planned maximum follow-up time) after last dose of treatment including rescue, regardless of study period. Listings will include all safety data.

For the 16-week interim lock, all safety data up to the Week 16 visit and at time of the interim lock were included in the safety analysis. Safety data from patients who permanently discontinued study drug prior to time of the interim lock will be included in the interim lock safety analysis up to 30 days post-last dose of the study drug.

For the final DBL, safety data from the Week 16 visit date up to the end of the study will be included in the safety analysis. Safety data from patients who permanently discontinued study drug will be included in the safety analysis up to 30 days post-last dose of the study drug.

The following will be analyzed for the final DBL, based on Week 16 Responders:

- summary of study drug exposure
- overview of adverse events
- overview of infections
- summary of temporary interruptions of study drug
- summary of treatment-emergent adverse events
- serious adverse events, summary and listing, and
- adverse events leading to permanent discontinuation of study drug, summary and listing.

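### Interim safety tables that run past Week 16 are set up as crude percentages with Fisher's test, although follow-up after Week 16 depends on response and arm

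*SAP*

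**What the plan says.** **Follow-up of the interim safety groups.** The treatment-group table in Section 6.2.2 describes each arm as "followed to data cut (interim CSR". A later paragraph of that section runs the interim safety analysis to Week 16 and takes only certain analyses, not identified, to the data-cut date. Section 6.14 reads more widely: "all safety data up to the Week 16 visit and at time of the interim lock were included in the safety analysis". Section 6.14.2 defines the period for treatment-emergent events as the treatment period plus up to 30 days off drug, without a Week 16 cut, and Section 5 makes the treatment period 104 weeks. Section 6.14.1 expects some exposure of 112 days or more at the interim lock.

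**Measure and test.** Section 6.14.2 reports adverse events as n/N percentages of the safety population. Section 6.2.4 says that Fisher's "exact test will be used to test the difference between each baricitinib dose and placebo in proportion of patients experiencing adverse events".

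**Who stays after Week 16.** Section 5 says that "those patients who met IGA 0 or 1 and who have not required rescue therapy prior to Week 16 will be allowed to continue"; all others leave the study. Section 6.2.2 expects few placebo responders beyond that point and for this reason makes later efficacy descriptive. It gives no matching rule for safety.

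**Use of exposure.** Section 6.14.1 reports patient-years per arm. Incidence rates appear in Section 6.17.1, for the data monitoring committee, and in Section 6.14.5.6, for infections of special interest at the final analysis. None is specified for the interim study report.

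**The concern.** At Week 16 every arm has the same planned follow-up, so crude percentages compare like with like. After Week 16, time at risk depends on having responded without rescue, which the drug is meant to influence. A crude percentage then mixes the event rate with the length of observation, and Fisher's test cannot separate them. If the true rates are equal, the arm with more responders tends to show more patients with events.

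The interim lock matters because the final lock covers Week 16 responders only and drops the common-event, laboratory, vital-sign and special-interest analyses (Sections 6.14.2.1, 6.14.3, 6.14.4 and 6.14.5). The interim lock therefore carries this study's main placebo-controlled safety comparison.

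**Working it through.** **The plan's own figure.** The SAP gives no figure on this point. Its sample-size statement supplies the arm size and a stand-in for the shares continuing, so I checked that first. Section 5 gives "approximately 150 patients per group". Section 6.1 claims "at least 68% power", "assuming a 10% placebo and 20% baricitinib 2-mg response rate for the primary endpoint EASI75 using a Chi-squared test". Alpha there is 0.05, two-sided. With pooled variance under the null:

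Power = Φ[(0.10·√150 − 1.960·√(2·0.15·0.85)) / √(0.10·0.90 + 0.20·0.80)] = Φ[(1.2247 − 0.9897)/0.5] = Φ(0.470) = 68.1%.

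The stated power reproduces.

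**Model for a data-cut table with equal true event rates.**
- Week 16: t0 = 112/365.25 = 0.3066 years.
- Event rate in all arms (assumed): λ = 0.5 per patient-year.
- Share continuing, r (assumed): 10% placebo versus 20% baricitinib, borrowing the EASI75 rates because the SAP gives none for unrescued IGA 0/1; and 5% versus 25% as a wider contrast.
- Extra follow-up for those continuing, x (assumed): 0.5 or 1.0 year, with no dropout.
- Off-drug follow-up for those leaving at Week 16, f: 0, or 30/365.25 = 0.0821 years if all contribute the full 30 days.

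Crude proportion = (1−r)·[1−exp(−λ(t0+f))] + r·[1−exp(−λ(t0+x))].

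Components: a patient leaving at Week 16 has probability 0.1421 (f = 0) or 0.1767 (f = 30 days). A continuing patient has 0.3319 (x = 0.5) or 0.4797 (x = 1.0).

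Example, 10% versus 20%, x = 0.5, f = 0: placebo 0.9·0.1421 + 0.1·0.3319 = 0.161; baricitinib 0.8·0.1421 + 0.2·0.3319 = 0.180; ratio 1.12.

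| Continuing (placebo vs baricitinib) | Extra years | Without 30-day follow-up | With 30-day follow-up |
|---|---|---|---|
| 10% vs 20% | 0.5 | 16.1% vs 18.0%, ratio 1.12 | 19.2% vs 20.8%, ratio 1.08 |
| 10% vs 20% | 1.0 | 17.6% vs 21.0%, ratio 1.19 | 20.7% vs 23.7%, ratio 1.15 |
| 5% vs 25% | 0.5 | 15.2% vs 19.0%, ratio 1.25 | 18.4% vs 21.5%, ratio 1.17 |
| 5% vs 25% | 1.0 | 15.9% vs 22.7%, ratio 1.42 | 19.2% vs 25.2%, ratio 1.32 |

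The true rate ratio is 1.00 in every row. Cutting at Week 16, or dividing by time at risk, returns 1.00.

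**Effect on Fisher's test.** By exact enumeration with 150 per arm, 10% versus 20% continuing, no 30-day follow-up and equal rates, the chance of a significant result against baricitinib at two-sided 0.05 is:
- λ = 0.3: 1.6% when cut at Week 16, 3.8% with 26 extra weeks, 6.7% with 52.
- λ = 2: 2.1% when cut at Week 16, 11.2% with 52 extra weeks.

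**The case against.** A reader might infer that all interim safety comparisons are distorted and that the better arm will look less safe. The SAP does not support that. Section 6.2.2 stops the interim safety analysis at Week 16 apart from the unnamed data-cut analyses, and a table cut there is unaffected.

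Four further points count on the other side:
- Section 6.2.4 is a general methods paragraph, and no sentence says the data-cut tables carry Fisher tests. That is fair. But it is the rule the SAP gives for categorical safety data, and nothing exempts these tables.
- The Section 6.14 sentence that sets the default data period has a gap in the text available. It is not held against the plan; the point rests on other sentences.
- The SAP refers to separate compound-level safety standards, which might name these analyses or use rates. They are not available here. Within the SAP, the scope in Section 6.2.2 and the wider wording in Sections 6.14 and 6.14.2 still do not agree.
- The size depends on assumptions. Patients who worsen to IGA 3 or more leave after Week 16, which shortens the extra time, and responders may have a different event rate from other patients. Both are right, so the ratios are illustrations.

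The SAP also reports patient-years per arm, so a reader could see unequal exposure. That display does not correct the percentages or the p-values.

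**Conclusion.** The point holds for interim safety tables run past Week 16 and for no others. For them the SAP specifies a measure and test that ignore time at risk, while its own design makes that time depend on response and therefore on arm. It also leaves open which tables these are.

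The likely size is modest: a spurious ratio of about 1.08 to 1.19 at 10% versus 20% continuing, and 1.17 to 1.42 at 5% versus 25%. This assumes 0.5 events per patient-year in every arm, 0.5 to 1.0 extra years without dropout, and the same event rate in responders as in others. None of these is in the SAP. A higher crude percentage on baricitinib is a tendency under these assumptions, not a predicted result. The change is worth making, but the point does not undermine the Week 16 safety comparison.

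**What to change.** 1. Reconcile Sections 6.2.2, 6.14 and 6.14.2, and list the analyses that run to the data cut.
2. Base between-arm percentages and Fisher tests on Weeks 0 to 16, plus the stated 30-day follow-up for patients who stopped. State how that window treats patients who leave at Week 16. If they contribute 30 more days while continuing patients are cut at Week 16, a small imbalance the other way remains. At 0.5 per patient-year and 10% versus 20% continuing: placebo 0.9·0.1767 + 0.1·0.1421 = 17.3%, baricitinib 0.8·0.1767 + 0.2·0.1421 = 17.0%, ratio 0.98.
3. Report data-cut results by arm as exposure-adjusted incidence rates with 95% CIs, not as Fisher-tested crude proportions.

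Section 6.2.1 records the interim lock as already executed. The change therefore applies by relabelling or supplementing the interim tables, marked as made after unblinding, and in any further safety locks. The cost is wording and a rate column, since patient-years of exposure are already planned. The downside is a separate table for events after Week 16.

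### Off-drug safety events that occur after the interim data cut, in patients who left at Week 16 and did not enter Study JAIX, have no assigned study-report output

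*SAP*

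**What the plan says.** Four sets of rules in the SAP bear on this point.

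- **Off-drug window.** Section 6.14: "Follow-up data is defined as all data occurring up to 30 days (planned maximum follow-up time) after last dose of treatment". Section 6.14.2 uses the same span for treatment-emergent events. Footnote c to the design figure in Section 5 places the follow-up visit: "Occurs approximately 28 days after the last dose of investigational product".
- **Week 16 lock.** Section 6.2.1: "An unblinded interim lock was executed after all patients have completed the Week 16 visit (Visit 8) or discontinued". Section 6.2.2 says that at this lock "the safety analysis will be up to Week 16 and selected analyses up to the data cut date"; it does not name the selected analyses or give the date. Section 6.14 says that data from patients who permanently stopped study drug before the lock "will be included in the interim lock safety analysis up to 30 days post-last dose of the study drug".
- **Final lock.** Under Section 6.2.1 this lock waits until every patient has completed the follow-up visit, permanently discontinued or moved to Study JAIX. Section 6.2.2 then restricts its output: "For the final DBL, both efficacy and safety summaries will use the Week 16 Responders population". Section 6.14 lists the final-lock safety outputs, including the summaries and listings of serious adverse events and of adverse events leading to permanent discontinuation, all on that population. By definition it holds only patients who go on beyond Week 16.
- **Locks in between.** Section 6.2.1, on the 4-month safety update lock and further safety locks: "Clinical study reports will not be developed based on these safety locks".

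Under Section 5, everyone who is not an unrescued IGA 0 or 1 responder leaves the study at Week 16 and may be eligible for open-label Study JAIX.

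**The concern.** A patient who leaves at Week 16 and does not enter Study JAIX has an off-drug window that runs to about Week 20. The Week 16 lock does not require that window to be closed. The final lock does hold the completed follow-up, but its safety outputs exclude this patient by definition. A serious event, death or other event late in the window can therefore be collected, fall inside the SAP's own analysis period, and still be assigned to neither study report.

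At stake is whether the treatment-plus-30-days incidence in the Week 16 report is complete for the last patients to leave and, if it is not, whether anything later completes it. As written, the answer turns on a cut date that the SAP does not state.

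**Working it through.** The SAP gives no figure on this point, so there is none to reproduce. The check has two parts.

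**1. Where each kind of event is assigned** (patients who did not continue past Week 16)

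| Event | Week 16 report | Safety locks | Final report |
|---|---|---|---|
| On treatment | Yes | No study report | Excluded by population |
| Off drug, within 30 days, on or before the interim cut | Yes (6.14) | No study report | Excluded by population |
| Off drug, within 30 days, after the interim cut | Not yet available | No study report | Excluded by population |

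Only the last row has no assigned output.

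**2. How many patients could have an unfinished window at the cut**

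With even accrual:

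n = 450 × p × q × max(0, F − L) / T

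From the SAP:
- 450 planned patients (Section 6.1).
- F = 28 days (follow-up visit, Section 5) or 30 days (analysis window, Section 6.14).

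Assumed, because the SAP gives none of these:
- p, the share not continuing past Week 16: 0.80 to 0.95.
- q, the share of those not entering JAIX: 0.10 to 1.00.
- T, the accrual period: 180 to 540 days.
- L, the days from the last Week 16 departure to the data cut: 0 to 30.

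Largest case, F = 30, L = 0, T = 180, p = 0.95, q = 1: 450 × 0.95 × 1 × 30/180 = 71.2.

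Smallest case with no lag, F = 28, T = 540, p = 0.80, q = 0.10: 450 × 0.80 × 0.10 × 28/540 = 1.9.

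High setting (p = 0.95, q = 1):

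| Lag L | F = 28, T = 180 | F = 30, T = 180 | F = 30, T = 365 | F = 30, T = 540 |
|---|---|---|---|---|
| 0 days | 66.5 | 71.2 | 35.1 | 23.8 |
| 14 days | 33.2 | 38.0 | 18.7 | 12.7 |
| 28 days | 0 | 4.8 | 2.3 | 1.6 |
| 30 days | 0 | 0 | 0 | 0 |

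A middle setting (p = 0.90, q = 0.50, F = 30, L = 0) gives 33.8, 16.6 and 11.2 for T = 180, 365 and 540.

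These are patients with an unfinished window, not events. The formula treats everyone as leaving at Week 16. Patients who stopped earlier tend to have finished their window sooner, so the counts lean high.

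**Share of off-drug time missed.** With L = 0, a fraction F/T of these patients is affected and each misses half the window on average, so the missed share is F/(2T). With F = 30 this is 30/360 = 8.3% for T = 180 and 30/1080 = 2.8% for T = 540.

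**The case against.** The strongest reply is that the SAP never says the Week 16 lock closes early. Section 6.2.1 gives a condition, which fixes the earliest moment and not a date. Section 6.2.2 refers to a separate data cut. A cut 30 days or more after the last departure leaves no gap. The 30-day rule in Section 6.14 is written for patients who have stopped drug by that lock, so their off-drug events up to the cut are in the Week 16 report. All of this stands, and it makes the point conditional.

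A reader might infer that the off-drug events of non-continuing patients appear in no study-report table, or that this affects most of the patients who left at Week 16. The documents do not support either reading. Events up to the cut are tabulated. Even with no lag and a six-month accrual, only 30/180, or about 17%, of those outside JAIX have an unfinished window. Patients who enter JAIX may have no off-drug window in this study.

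The objection can also point to general sentences. Section 6.14 says that listings cover all safety data, Section 6.14.2.2 promises a listing of deaths during the study, and Section 6.20 provides a registry summary of serious events. The first two leave some room for a listing to catch these patients. However, the final-lock list in Section 6.14 expressly limits the serious-event and discontinuation listings to Week 16 Responders, and the registry output is not a study-report table. These sentences soften the gap without closing it.

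**Conclusion.** The point holds in conditional form. The SAP undertakes to include up to 30 days of post-dose safety data at the Week 16 lock. Its trigger does not guarantee that those data exist for the last patients to leave, and its final-lock rules do not recover the remainder. What has no assigned study-report output is an off-drug event after the interim cut, in a patient who neither continued past Week 16 nor entered JAIX.

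The exposed number is zero if the cut came 28 days (follow-up visit) or 30 days (analysis window) or more after the last departure. With no lag it ranges from about 2 to about 70 over the assumed accrual periods, non-continuing shares and JAIX entry rates, none of which the SAP gives. The number of events would be smaller, and the documents do not allow it to be estimated. The point still merits a change, because complete reporting of deaths and serious events should not rest on an unstated date when the final database already holds the data.

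**What to change.** Either of two changes closes the gap.

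1. In Sections 6.2.2 and 6.14, add to the final lock, for safety-population patients who did not continue past Week 16, a listing of events with onset after the interim data cut and up to 30 days after last dose. Add a brief summary of deaths, serious adverse events and adverse events leading to discontinuation over the same span. Keep the Week 16 Responders outputs as planned.
2. Or fix the interim data cut at 30 days or more after the last non-continuing patient's last dose. This SAP version describes the Week 16 lock as already executed, so here that means stating the cut that was used. If it meets the condition, no further output is needed.

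In both cases, reconcile Sections 6.2.1, 6.2.2 and 6.14 so that the lock trigger, the analyses run to the data cut and the 30-day rule describe the same data span. A full rerun of all adverse-event tables on the safety population is optional.

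The cost is a few extra outputs in the abbreviated study report, produced with existing programs on data already held.
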